3.12 SAFETY ANALYSES

3.12.1 Exposure of Study Medication

Exposure to RO7234292 and placebo over the course of the study will be summarized using descriptive statistics.

Duration of treatment exposure (in days) to study drug will be calculated as:

Last follow-up visit date – treatment start date +1

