4.9 SAFETY ANALYSES

Following the iDMC recommendation, effective 22 March 2021, no further study treatment was administered in this study. Patients in the study were continued to be followed for safety and efficacy outcomes until study completion.

All safety endpoints will be analyzed overall, i.e., disregarding if data was collected during on-treatment period or during off treatment follow-up period. On-treatment period is defined as time from first dose to last dose plus 5 months. Off-treatment follow-up period is defined as the time more than 5 months after last dose of study drug.

Analyses addressing the on-treatment period and off-treatment follow-up period are described in Section 5.

For all safety endpoints, if not stated otherwise, the baseline will be defined as the last assessment prior to the first lumbar puncture procedure or last assessment on Day 1, whichever occurred first.

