4.9.1 Exposure of Study Medication

Exposure to RO7234292 and placebo over the course of the study will be summarized using descriptive statistics for the safety evaluable population and the PK population. The duration of exposure, defined as number of days from first dose of study treatment to last dose plus 5 months (i.e., 152 days) as well as the duration of the off treatment follow-up period will be summarized descriptively.

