Upon completion of the screening period, eligible patients will be randomly allocated in a 1:1:1 ratio to receive RO7234292 every 4 weeks (RO7234292 Q4W arm), RO7234292 every 8 weeks (RO7234292 Q8W arm), or placebo Q4W (placebo arm) by IT injection. To maintain the study blind and integrity, patients in the RO7234292 Q8W arm will also receive placebo (i.e., alternating doses of active drug and placebo).

Patients

will undergo safety and tolerability evaluations that include neurologic examinations, vital signs, ECGs, clinical laboratory tests, MoCA, C-SSRS, neuroimaging assessments (neurologic safety sequences), and adverse events including related concomitant medications.

Patients who complete the treatment period will return to the clinic for an end-of-treatment visit at Week 101. Patients will then be given the option on an individual basis of receiving RO7234292 in an OLE study (BN40955) upon completion of Study BN40423, provided they meet eligibility criteria and the data from the ongoing RO7234292 program support continued development. Approval of the open-label extension (OLE) study must also be granted by the relevant competent authority and Ethics Committee (EC)/Investigational Review Board (IRB).

All patients who discontinue study treatment prematurely but do not withdraw consent for continued participation in the study will return to the clinic for study visits at Weeks 53 and 69 (if not already completed) for collection of at least the data for the primary and secondary endpoints. If the early treatment termination visit falls within ± 30 days of either scheduled visits at Week 53 or Week 69, then only early treatment termination visit will be considered. The early treatment termination visit should be performed 28 days (± 3 days) after the last dose. Patients will also attend the scheduled end-of-treatment visit at Week 101.

An independent Data Monitoring Committee (iDMC) and independent Data Coordinating Center (iDCC) will be employed to monitor and evaluate patient safety throughout the study as well as to evaluate evidence of early efficacy.

Number of Patients

Approximately 660 patients with HD will be enrolled in this global study.

Target Population

Inclusion Criteria

Patients must meet the following criteria for study entry during screening (some will be reassessed at baseline):

- Signed Informed Consent Form
- Age 25 to 65 years, inclusive, at the time of signing Informed Consent Form

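### SAP Version 1 labels time on study as duration of treatment exposure: the formula uses no dosing date after the first and sets no limit on time after the last dose

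*SAP*

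**What the plan says.** SAP Version 1 covers only the Original Design Cohort, the 108 patients randomized before enrollment under Protocol Versions 1-3 stopped. It is still the operative plan for them, because Section 1 of SAP Version 3 refers the reader to it for that cohort.

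Section 3.12.1 introduces the variable with "Duration of treatment exposure (in days) to study drug will be calculated as" and then gives "Last follow-up visit date – treatment start date +1". It does not say which visit is the last follow-up visit, for example for a patient who moves to the open-label extension.

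For the later cohort, Section 4.9.1 of SAP Version 3 defines exposure as the "number of days from first dose of study treatment to last dose plus 5 months (i.e., 152 days", and summarizes the length of off-treatment follow-up separately. Section 4.9 of Version 3 uses the same window for safety: "On-treatment period is defined as time from first dose to last dose plus 5 months".

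The protocol synopsis in Appendix 1 of Version 1 provides for visits after dosing has stopped. It says "The early treatment termination visit should be performed 28 days" after the last dose, and that patients who stop early but do not withdraw consent "will return to the clinic for study visits at Weeks 53 and 69 (if not already completed", with a further visit at Week 101. The schedule in Appendix 2 adds a safety follow-up at Week 117.

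**The concern.** The label promises a treatment quantity and the formula delivers a follow-up quantity. Two patients with very different numbers of injections get the same duration if they were last seen the same number of days after the start. A patient who stops early and keeps attending accrues stated exposure at the same rate as one who is still being dosed.

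Elsewhere Version 1 keeps these ideas apart. Section 3.2 counts discontinuation from treatment, discontinuation from the study and rollover, and the suicidality shift table in Section 3.12.5 separates treatment from post-treatment time. Only the exposure formula merges them.

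At stake is the exposure summary for the only cohort with a monthly active arm. It is the one exposure variable that Section 3.12.1 defines; number of injections is not named. A reader who uses the table to judge how much drug lies behind the adverse event percentages would be reading follow-up time. The two cohorts of the study would also report a quantity of the same name on different bases.

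**Working it through.** The plan states no exposure figure, so there is nothing to reproduce. The check is day arithmetic on the Version 1 schedule.

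**Inputs.** Treatment start is Day 1, and Week w falls on Day 7(w − 1) + 1. The 28-day interval to the early treatment termination visit and the Week 117 safety follow-up come from Appendices 1 and 2 of Version 1. The 152-day window comes from Section 4.9.1 of Version 3. The last-dose and last-visit dates are assumptions; actual dates are not in the documents.

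**Formulas.** Let L be the day of the last dose and F the day of the last follow-up visit.

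- (a) Version 1: F − 1 + 1 = F
- (b) First to last dose: L − 1 + 1 = L
- (c) Version 3 rule, counted inclusively: L − 1 + 152 + 1 = L + 152

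Hence (a) − (b) = F − L, and (a) − (c) = (F − L) − 152.

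| Illustrative patient | L | F | (a) | (b) | (c) | (a) − (c) |
|---|---|---|---|---|---|---|
| Last dose Week 21, last seen 28 days later | 141 | 169 | 169 | 141 | 293 | −124 |
| Last dose Week 5, last seen 152 days later | 29 | 181 | 181 | 29 | 181 | 0 |
| Last dose Week 5, last seen Week 37 | 29 | 253 | 253 | 29 | 181 | +72 |
| Last dose Week 5, last seen Week 53 | 29 | 365 | 365 | 29 | 181 | +184 |
| Last dose Week 97, safety follow-up Week 117 | 673 | 813 | 813 | 673 | 825 | −12 |

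**Reading.** Against dosing duration, Version 1 is longer whenever any visit follows the last dose. Against the Version 3 rule the sign turns at 152 days after the last dose. Rows 3 and 4 show that the Version 1 figure keeps growing after dosing stops, while (b) and (c) stay fixed.

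**Limits of the illustration.** Week 37 is an assumed last visit, not one the synopsis names for early stoppers. Week 53 is named there, but Section 3.7 of Version 1 says that few patients reached the 9-month visit (Week 37 in Appendix 2). The last row describes a full schedule that, according to Version 1's introductory text, no patient in this cohort completed.

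**Effect of truncation.** If the patient in the first row left the study at that visit (Day 169), the Version 3 window truncated at withdrawal or rollover would give min(293, 169) = 169 days, the same as Version 1.

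**The case against.** The strongest reply is that a reader might infer that drug-free time is being counted, so that the reported exposure is inflated. The documents do not support that. Version 3 counts the 152 days after the last dose as exposure and as on-treatment time, and Appendix 2 of Version 1 collects all adverse events until 5 months after the final dose. Nowhere do the documents end exposure on the date of the last dose. Ending it there would give a single-dose patient 1 day of exposure to a drug injected every 4 or 8 weeks. This stands, so last dose alone is not the right yardstick.

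A reader might also infer that early stoppers are systematically credited with more exposure than patients who kept dosing. That is not shown either. The documents do not say how many patients stopped early and stayed in follow-up, or how long after the last dose rollover patients were last seen.

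The remaining objections limit the impact. Adverse event percentages in Section 3.12.2 are per patient, and no exposure-adjusted rate is specified. The definition of a treatment-emergent event there has no end date, so time from first dose to last visit is a reasonable time at risk for that numerator. The two SAP versions are separate plans for separate cohorts, so the differing formulas are an inconsistency of convention, not a contradiction within one analysis.

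None of this rescues the label. A formula without a last-dose date cannot be called exposure under either convention, and nothing stops it growing after dosing has ended.

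**Conclusion.** The point holds as a mismatch between label and formula. Section 3.12.1 of SAP Version 1 defines time on study from first dose and calls it duration of treatment exposure.

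What is certain is structural: no dosing date after the start enters the formula, and time after the last dose is unbounded for a patient who stops dosing and keeps attending. What is not established is a size or direction for this cohort. Whether the figure overstates or understates exposure depends on the yardstick and, under the Version 3 rule, on whether the last visit fell more or less than 152 days after the last dose. Those dates are not in the documents.

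The consequence is modest: one descriptive table and the context in which per-patient adverse event percentages are read. No efficacy result changes. The correction is still worth making because it is cheap and the table as labelled would mislead.

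**What to change.** In Section 3.12.1 of SAP Version 1:

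- Define duration of exposure from the first and last dose dates, with the same 152-day post-dose window as Section 4.9.1 of Version 3, truncated at death, withdrawal or rollover. If another window is preferred, state it and give the reason for departing from Version 3.
- Keep the present formula, renamed time on study, as a separate line, and say which visit counts as the last follow-up visit, including for patients who enter the extension.
- Tabulate the number of active injections received per patient, by arm. A duration truncated at rollover will not by itself distinguish one injection from several; the count will.

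The cost is a wording change, one re-derived variable from dosing dates and one added tabulation. Individual exposure figures may become shorter or longer than under the present formula.

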3.12.2 Adverse Events

All treatment-emergent adverse events (TEAEs) and serious adverse events (SAEs) will be summarized for each treatment arm and for all patients using the Medical Dictionary for Regulatory Activities (MedDRA) coding by system organ class, preferred term, relationship to study drug, and severity. Percentages presented in AE tables will display the percentage of patients within a treatment arm experiencing the AE at least once.

An AE will be regarded as TEAE if the event occurs after the first dose of treatment or if event occurs before the first dose of treatment and worsens after the first dose.

Adverse events that occur before first dose administration and are not related to study procedure will be included in data listings only. SAEs and non-serious AEs that lead to treatment discontinuation or treatment interruption will be listed separately. Selected adverse events, for instance procedure related AEs, will be summarized and listed separately.

3.12.3 Laboratory Data

Abnormal laboratory outcomes will be reported. A summary of the number and percentage of patients with abnormal laboratory outcomes will be produced at each visit and overall by treatment group.

Absolute values and change from baseline values for all laboratory assessments will be summarized by descriptive statistics at each visit by treatment group.

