4.9.3 Laboratory Data

Abnormal laboratory outcomes will be reported. A summary of the number and percentage of patients with abnormal laboratory outcomes will be produced at each visit by treatment group.

Absolute values and change from baseline values for all laboratory assessments will be summarized by descriptive statistics at each visit by treatment group. The baseline for the laboratory, except for the CSF safety lab parameters, will be defined as the last assessment prior to the first lumbar puncture or last assessment on Day 1, whichever occurred first. For the CSF safety lab parameters, the baseline will be defined as the last assessment prior to the first dosing administration or last assessment on Day 1, whichever occurred first.

For the measurement reported as ' $<x$ ' or ' $>x$ ', the value will be set to x .

In addition, the shifts (relative to the normal range) from baseline to the minimum and maximum post-baseline values will be presented. If a subject is missing a baseline value but had a post-baseline value, then the baseline assessment is labeled as

"unknown". Likewise, if a subject had a baseline value but had no post-baseline values, then the minimum and maximum are labeled as "unknown".

The number of patients with abnormal and marked abnormal absolute values for the CSF safety labs, according to the parameter ranges presented in [Table 1](#), will be summarized by treatment and visit.

Table 1 CSF Safety Laboratory Normal Ranges

Parameter	Low	Normal	High	Marked High
Glucose (mmol/L)	<2.2	2.2-3.9	> 3.9	> 4.4
Protein (g/L)	<0.15	0.15-0.5	> 0.5	
Erythrocytes (cells/ μ L)		0	>0	> 5
Leucocytes (cells/ μ L)		0-5	>5	

CSF = cerebrospinal fluid.

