3.3 BASELINE DEFINITION

The baseline will be defined as the last non-missing assessment prior to the randomization date or the first dosing date, whichever is the latest.

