3.12.4 Vital Signs and ECG

Absolute values and change from baseline values for vital signs and ECG data will be summarized by descriptive statistics at each visit by treatment group.

A listing of patients meeting any of the abnormality criteria as presented in [Table 3](#) (according to Roche data analysis standards [GDSR]) will be provided.

Abnormal findings and clinical significance for the finding for ECG parameters will be listed.

Table 3 Vital Signs Ranges

Parameter	Low	Normal	High
Pulse/HR (bpm)	<60	60-100	>100
SBP (mmHg)	<90	90-130	>130
DBP (mmHg)	<60	60-80	>80
Temperature (C)	<36.5	36.5-37.5	>37.5
RR (bpm)	<8	8-20	>20

DBP= diastolic blood pressure; HR=heart rate; RR=refractory rate; SBP=systolic blood pressure.

Note: The boxplots of vital signs and ECG by visit and by treatment group will be provided.

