3.12.7 Safety MRI

Clinical assessments from the safety MRI will be summarized by descriptive statistics at each visit by treatment group. In addition, a shift table will be created to demonstrate the change in safety MRI status from baseline to post-baseline.

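### SAP Version 1, Section 3.12.3: the abnormal-laboratory counts for the Original Design Cohort do not separate abnormalities present before the first dose from new ones, which dilutes the comparison between arms

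*SAP*

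**What the plan says.** All of this concerns SAP Version 1, which covers the Original Design Cohort only, unless stated otherwise.

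- **Laboratory counts (Section 3.12.3).** "A summary of the number and percentage of patients with abnormal laboratory outcomes will be produced at each visit and overall by treatment group". Abnormal is not defined in relation to baseline, and the overall count is not restricted to samples taken after dosing.
- **Other laboratory output (Section 3.12.3).** "Absolute values and change from baseline values for all laboratory assessments will be summarized by descriptive statistics at each visit by treatment group". No shift table is named.
- **Vital signs (Section 3.12.4).** The same kind of descriptive summary is planned ("Absolute values and change from baseline values for vital signs and ECG data will be summarized by descriptive statistics at each visit by treatment group"), with boxplots by visit and arm. There is also a listing: "A listing of patients meeting any of the abnormality criteria as presented in" Table 3.
- **Baseline (Section 3.3).** "The baseline will be defined as the last non-missing assessment prior to the randomization date or the first dosing date, whichever is the latest". The reference value needed to separate old from new abnormalities is therefore already defined.
- **Other safety data.** Adverse events have a treatment-emergent rule (Section 3.12.2: "An AE will be regarded as TEAE if the event occurs after the first dose of treatment or if event occurs before the first dose" and then worsens). The C-SSRS section (3.12.5) has emergent endpoints and a shift table. For safety MRI (Section 3.12.7), "a shift table will be created to demonstrate the change in safety MRI status from baseline to post-baseline".
- **Version 3, for the later cohort (Section 4.9.3).** For laboratory data, "the shifts (relative to the normal range) from baseline to the minimum and maximum post-baseline values will be presented".

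**The concern.** The safety endpoint in Version 1 Section 2.2.4 is change from baseline in laboratory results, CSF findings included. The patient-level output in Section 3.12.3 does not answer that question. It mixes patients who were out of range before dosing with patients who became so afterwards.

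The Version 1 schedule of assessments (Appendix 2) has hematology and chemistry drawn at screening, Day -1 and Day 1, and treatment-day assessments are done before dosing. Read literally, the overall count could include a patient whose only abnormal value came before any drug.

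Some baseline abnormality is to be expected. The entry criteria in the Version 1 synopsis exclude laboratory abnormalities that are clinically significant and judged to preclude safe participation, not every out-of-range value. They also admit platelet counts of 125,000 to 150,000 under a condition, as an exception to the rule excluding counts below the lower limit of normal.

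Two things are at stake. Persistent baseline abnormalities add the same amount to each arm on average, so they shrink the ratio and the difference between arms. With about 36 per arm, a chance imbalance at baseline also enters the count directly. This matters because the Original Design Cohort is the only cohort in the document with active drug every 4 weeks, and it is excluded from the primary safety analysis of the later design. Its own tables are where a laboratory signal at that frequency would be looked for.

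**Working it through.** The plan gives no figure on this point to reproduce. The calculation below is an illustration.

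**Inputs from the document.** 108 patients allocated 1:1:1 (Version 1 Section 2), so n = 108/3 = 36 per arm.

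**Assumed inputs, not in the document.** The risk of a new abnormality among patients normal at baseline is 5% on placebo and 25% on active. A fraction b of patients in each arm is abnormal at baseline and stays abnormal; b is varied from 2% to 30%.

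**Formulas.**

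- Counted as planned: rate in an arm = b + (1 - b) × new risk, with n = 36.
- Counted among patients normal at baseline: rates 5% and 25%, with n = 36(1 - b).
- Signal-to-noise ratio in both cases: z = (p1 - p0) / sqrt[p0(1 - p0)/n + p1(1 - p1)/n].
- Loss = 1 - z(planned)/z(normal at baseline).
- Chance imbalance with no drug effect: probability that two independent Binomial(36, b) counts differ by 4 or more.

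**Worked case, b = 10%.** The planned rates are 0.10 + 0.90 × 0.25 = 32.5% and 0.10 + 0.90 × 0.05 = 14.5%. The ratio is 2.24 instead of 5.0, and the difference is 18 points instead of 20. Then z = 0.18 / sqrt(0.325 × 0.675/36 + 0.145 × 0.855/36) = 1.84. Among patients normal at baseline, n = 32.4 and z = 0.20 / sqrt(0.25 × 0.75/32.4 + 0.05 × 0.95/32.4) = 2.35. The loss is about 22%.

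| b | Planned rates, active vs placebo | Ratio | z as planned | z, normal at baseline | Loss | Gap of 4 or more patients by chance |
|---|---|---|---|---|---|---|
| 2% | 26.5% vs 6.9% | 3.84 | 2.31 | 2.45 | 6% | 0.6% |
| 5% | 28.8% vs 9.8% | 2.95 | 2.11 | 2.41 | 13% | 6% |
| 10% | 32.5% vs 14.5% | 2.24 | 1.84 | 2.35 | 22% | 17% |
| 20% | 40.0% vs 24.0% | 1.67 | 1.48 | 2.21 | 33% | 30% |
| 30% | 47.5% vs 33.5% | 1.42 | 1.22 | 2.07 | 41% | 37% |

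At b = 10, 20 and 30%, pre-existing cases make up b/(planned active rate) = 31, 50 and 63% of the abnormal patients in the active arm.

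**Would the same conditioning help the vital-sign listing?** I simulated four vital signs with assumed means (SD) of 36.6 (0.35) °C, diastolic 77 (9), systolic 122 (13) and pulse 72 (11), within-patient correlation 0.5 and six post-baseline visits. About 99% of patients meet some Table 3 limit at least once. Listing only those who go from within range at baseline to outside it still lists about 88%. The long listing comes mainly from how narrow the limits are, and conditioning on baseline barely shortens it.

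**The case against.** The strongest reply is that the plan does not ignore baseline. The same section plans change-from-baseline summaries for every laboratory assessment, by visit and arm. Counts by visit, set beside a randomized placebo arm, let a reader see a baseline imbalance if baseline visits are tabulated. The end of Section 3.6 also allows further unlisted analyses if a safety concern arises. The cohort is small and closed, its clinical-endpoint analysis is exploratory with descriptive p-values, and entry criteria may keep b low for several parameters.

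Most of this stands as mitigation. A reader might infer that the plan hides drug-related laboratory changes. The documents do not support that; the fair word is dilutes. What the reply does not supply is a view of which patients crossed from normal to abnormal. Group summaries of change do not give that, a few large shifts can vanish in a mean, and the clause on further analyses helps only once a concern has been noticed.

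A reader might also infer that Version 1 contradicts Version 3. It does not. They are separate plans for different cohorts, and Version 3 keeps an unconditioned abnormal-laboratory count of its own. Version 3 shows only that the sponsor has a suitable table.

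Finally, it is tempting to restrict the vital-sign listing to patients within range at baseline. That would drop anyone already out of range who then worsens, and no vital-sign shift table is planned that would keep them in view. By-arm summaries and boxplots are already planned there, and Appendix 2 of Version 1 directs new or worsened clinically significant vital-sign abnormalities to the adverse event form.

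**Conclusion.** The point holds for the laboratory counts in Version 1 Section 3.12.3. They do not separate pre-existing from new abnormalities, the overall count is not limited to post-dose values, and nothing else in Version 1 fills the gap at patient level. Version 1 does make the distinction for adverse events, suicidality and safety MRI.

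The loss in signal-to-noise runs from about 6% to 41% for persistent baseline abnormality of 2% to 30%. It rests wholly on the assumed 5% and 25% risks and on every baseline-abnormal patient staying abnormal. For parameters screened tightly at entry, the lower end is more plausible. The effect is on how safety data are read, not on type I error. This is a cheap and worthwhile improvement; the document does not support a claim that safety signals would be missed. For vital signs, the listing should not be restricted.

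**What to change.** In Version 1 Section 3.12.3:

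1. Add the shift table that Version 3 Section 4.9.3 already specifies: baseline category against minimum and maximum post-baseline value, by arm.
2. State that the overall count uses only values after the first dose.
3. Present that overall count by arm and parameter for patients within range at baseline, using the Section 3.3 baseline. Patients abnormal at baseline remain visible in the shift table.

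In Section 3.12.4, keep the full vital-sign listing. At most, flag baseline status in it and add a by-arm summary of shifts from baseline to the worst post-baseline value.

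The cost is SAP wording and a few standard tables built on baseline values already collected. The downside is a smaller denominator for the count of new abnormalities, for example 36 × 0.8 = 28.8 per arm instead of 36 if 20% are abnormal at baseline.
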